### **7.2.2 Safety and Tolerability Assessments**

Safety assessments are specified below with the assessment schedule detailing when each assessment is to be performed.

For safety evaluations, baseline is defined as assessments done on Day 1 prior to the first dose of study treatment.

The investigator will report any vital signs considered clinically significant in the eCRF. For details on AE collection and reporting refer to AE [Section 8.1](#).

#### **7.2.2.1 Physical Examinations**

A complete physical examination will be performed at the screening visit. This examination excludes pelvic, rectal, and breast examinations unless clinically indicated.

---

A symptom directed physical examination will be performed at other visits, as specified in the SoA and as clinically indicated.

Investigators should pay special attention to clinical signs related to COVID-19, to ongoing medical conditions and to previous serious illnesses.

### **7.2.2.2 Vital Signs**

Vital signs will be measured as specified in the SoA and as clinically indicated. Vital sign measurements to be measured in the sitting position after 5 mins rest if applicable. Vital signs include:

- Height and weight are only needed at screening
- Body temperature
- Systolic BP, diastolic BP
- Pulse rate
- Respiration rate
- Saturation of peripheral oxygen
- Supplemental oxygen flow rate, FiO2 if known, and method of delivery, if applicable or clinical indicated.

Additional vital signs may be measured during the study if warranted, 12-ECG assessment as determined by the investigator.

### **7.2.2.3 Clinical Laboratory Tests**

Local clinical laboratory parameters will be used for the analysis of scheduled hematology, chemistry and other blood specimens collected as part of safety monitoring (as detailed in SoA) and the results will be collected in the eCRF, except for specific parameters which will be performed centrally by a Kintor designated laboratory (as detailed in Appendix 4).

Unscheduled assessments of these parameters can be performed more often as clinically indicated. It is preferable to use the same laboratory for all the assessments performed, especially for hematology.

Laboratory values obtained during the screening phase will be used to assess subject's eligibility.

The local laboratory must provide Kintor with a copy of the certification and a tabulation of normal ranges and units for all local laboratories used in the study.

Clinically significant abnormalities must be recorded as either medical history/current medical conditions or AEs as appropriate.

There are no specific notable range criteria for this study; however, the local and central laboratory will flag laboratory values falling outside of the normal range, on the local and central laboratory report (as applicable) (which the investigator should sign off) as per local practice, and the investigator will report any values considered clinically significant in the eCRF.

---

See [Appendix 4](#) for the list of clinical laboratory tests to be performed and the SoA for the timing and frequency.

All protocol-required laboratory assessments, as defined in Appendix 4 must be conducted in accordance with the laboratory manual and the [SoA](#).

Clinically significant abnormal laboratory findings are those which are not associated with the underlying disease, unless judged by the investigator to be more severe than expected for the subject's condition.

All laboratory tests with values considered clinically significantly abnormal during participation in the study or within 28 days after the dose of study intervention should be repeated until the values return to normal or baseline or are no longer considered clinically significant by the investigator or Sponsor. If such values do not return to normal/baseline within a period judged reasonable by the investigator, the etiology should be identified, and the Sponsor notified.

The investigator must review the laboratory report, document this review in timely manner, and record any clinically relevant changes occurring during the study in the AE section of the CRF.

The laboratory reports must be filed with the source documents.

If laboratory values from non-protocol specified laboratory assessments performed at the institution's local laboratory requires a change in subject management or are considered clinically significant by the investigator (e.g., SAE or AE or dose modification), report in the AE section of the CRF and this test is recorded as unscheduled visit in eCRF.

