### **GT0918-CN-1003**

The GT0918-CN-1003 was an open-label, randomized, Phase 2, multicenter study to evaluate the safety and efficacy in subjects with mCRPC. Total of 108 subjects were enrolled in the study and randomized in 1:1:1 ratio in to 100 mg, 200 mg and 300 mg cohorts: 100 mg (n=37), 200 mg (n=35) and 300 mg (n=36). Eighty-one subjects (75.0%) experienced  $\geq$  grade 1 drug-related AEs. Fourteen subjects (13.0%) experienced  $\geq$  Grade 3 AEs based on CTCAE v4.03. Most common drug-related AEs experienced  $\geq$  10% of subjects included aspartate aminotransferase increased (AST) (14.8%), alanine aminotransferase increased (ALT) (13.0%), white blood cell count decreased (12.0%), appetite decreased (13.0%), asthenia (17.6%), anemia (14.8%) and proteinuria (12.0%). Grade 3 asthenia, Grade 2 vomiting, Grade 2 hypokalemia, Grade 2 lung infection, Grade 3 anemia were the reported SAEs among all subjects. There were about 41.9% subjects who experienced Prostate-Specific Antigen (PSA) 50 reduction. Based on Response Evaluation Criteria in Solid Tumors (RECIST) 1.1 evaluation, the Overall Response Rate (ORR) was 15.8% and Disease Control Rate (DCR) was 78.9%.

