## **6.3 Dose Modifications**

### **6.3.1 Dose Discontinuation**

Any subject who develops  $\geq$  Grade 3 treatment emergent adverse events that are possibly, probably or definitely related to the study drug as assessed by the investigator will discontinue the treatment. There is no dose interruption or dose reduction in this study.

The treatment course should be continued if the subject becomes SARS-CoV-2 test negative or experiences complete resolution of symptoms.

For the subjects who are hospitalized during the study, the subject may continue the study treatment at the investigator's discretion based on individual benefit/risk assessment.

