### **8.1.2 Events NOT Meeting the AE Definition:**

- The following study-specific clinical events related to COVID-19 are exempt from AE reporting unless the investigator deems the event to be related to the administration of study drug:
  - Hypoxemia due to COVID-19 requiring supplemental oxygen;
  - Hypoxemia due to COVID-19 requiring non-invasive ventilation or high flow oxygen devices;
  - Respiratory failure due to COVID-19 requiring invasive mechanical ventilation or ECMO.
- Any clinically significant abnormal laboratory findings or other abnormal safety assessments which are associated with the underlying disease, unless judged by the investigator to be more severe than expected for the subject’s condition.
- The disease/disorder being studied or expected progression, signs, or symptoms of the disease/disorder being studied, unless more severe than expected for the subject’s condition.
- Medical or surgical procedure (e.g., endoscopy, appendectomy): the condition that leads to the procedure is the AE.
- Situations in which an untoward medical occurrence did not occur (social and/or convenience admission to a hospital).
- Anticipated day-to-day fluctuations of pre-existing disease(s) or condition(s) present or detected at the start of the study that do not worsen.

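### Laboratory abnormalities that both COVID-19 and GT0918 could explain can go unrecorded as AEs, because the disease exclusion in Protocol 7.2.2.3 and 8.1.2 has no drug-relatedness exception

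*Protocol*

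**What the plan says.** - **Protocol 7.2.2.3** defines the term: "Clinically significant abnormal laboratory findings are those which are not associated with the underlying disease, unless judged by the investigator". The one way back in reads in full: "unless judged by the investigator to be more severe than expected". It sets no numerical trigger ("There are no specific notable range criteria for this study"). Repeat testing and the reporting of out-of-range values both depend on clinical significance. The same section also tells the investigator to enter clinically relevant changes as AEs, without defining that term.
- **Protocol 8.1.2, laboratory bullet**, lists among events that are not AEs: "Any clinically significant abnormal laboratory findings or other abnormal safety assessments which are associated with the underlying disease", again excepting only those worse than expected.
- **Protocol 8.1.2, first bullet**, makes COVID-19 hypoxemia and respiratory failure "exempt from AE reporting unless the investigator deems the event to be related to the administration of study drug".
- **Protocol 8.1.3** gives a laboratory abnormality four alternative routes to AE status: clinical significance, resulting signs or symptoms, need for therapy, or need to change study treatment. Abnormalities that do not qualify are not to be reported as AEs.
- **Protocol 6.3.1** acts on Grade 3 or higher "treatment emergent adverse events that are possibly, probably or definitely related to the study drug as assessed by the investigator".
- **Protocol 8.2 and SAP 4.11.2 and 4.11.3** build the related-TEAE, AESI and time-to-AESI outputs from recorded AEs. Protocol 8.3.1 adds that an event that is not an AE cannot be an SAE.

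**The concern.** The sponsor wrote a drug-relatedness safeguard for respiratory events and left it out of the laboratory bullet directly below. The omission matters because laboratory effects are among the drug's known signals. Protocol 1.2.3.1.1 reports drug-related AST rise in 14.8%, ALT rise in 13.0% and white-cell decrease in 12.0% of subjects in GT0918-CN-1003, and one Grade 4 creatine phosphokinase rise is the stated exception to non-relatedness in GT0918-US-1001. SAP 4.11.3 names hepatic, hematological and creatine kinase events as AESIs.

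If a site attributes such a value to COVID-19, the decision that it is not an AE comes before any causality assessment. What is then lost is the AE record itself, and with it AESI and SAE status, the causality judgement, AE follow-up, and the step at which 6.3.1 would be considered. SAP 4.11.2 counts a missing relationship as related, but that cannot recover an event that was never entered.

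**Working it through.** No arithmetic applies, since the plan states no figure on this point. The check sets the passages side by side.

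**Step 1: the exceptions.**

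| Text | Effect | Back in if worse than expected? | Back in if attributed to drug? |
|---|---|---|---|
| 8.1.2, respiratory bullet | not an AE | no | yes |
| 8.1.2, laboratory bullet | not an AE | yes | no |
| 7.2.2.3, definition | not clinically significant | yes | no |

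**Step 2: the term itself.** Under 7.2.2.3 a disease-associated finding is clinically significant only if it is judged worse than expected. The laboratory bullet of 8.1.2 speaks of clinically significant findings that are disease-associated, and then spares those worse than expected. Applied literally together, the bullet excludes nothing. Sites must therefore read the term differently in the two sections. On either reading, a disease-associated value not judged worse than expected fails the first route of 8.1.3.

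**Step 3: the causality scale.** The classification that follows 8.1.2 calls an event *possibly* related when two of three criteria are met: plausible timing, not readily explained by the subject's clinical state, and a known pattern for the drug. A value that COVID-19 readily explains fails the second. It can still meet the first and third, which is two of three. *Possibly* is thus reachable, though not automatic.

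**Step 4: one case traced.** Take a Grade 3 ALT rise on treatment that the investigator associates with COVID-19 and does not judge worse than expected, with no symptoms, no therapy and no change to study treatment.

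1. 7.2.2.3: not clinically significant.
2. 8.1.2, laboratory bullet: not an AE, and suspected drug-relatedness does not bring it back.
3. 8.1.3: none of the four routes is met. The treatment-change route is circular if the only change in view is discontinuation under 6.3.1, because that rule first needs an AE.
4. Consequence: no TEAE record, no entry in the AESI or time-to-AESI outputs, no SAE status, and 6.3.1 is not reached.

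If any one of those conditions fails, the rise is an AE and reaches both the AESI tables and the 6.3.1 assessment.

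**Step 5: what remains.** Scheduled results go into the eCRF whatever their significance (7.2.2.3). Protocol 10.7.3 and SAP 4.11.4.1 tabulate new on-treatment Grade 3 or 4 values and shifts from baseline to worst value by arm, and list all results. Protocol 4.2 has the IDMC monitor unblinded safety data, including selected laboratory measurements.

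**The case against.** The strongest reply is that the gap is narrow and well backed up. A Grade 3 transaminase rise in an outpatient with mild to moderate disease is an obvious candidate for the worse-than-expected exception. Three of the four routes in 8.1.3 do not depend on clinical significance, and 7.2.2.3 separately asks for clinically relevant changes to be entered as AEs. Section 6.3.1 acts on AEs, so a non-AE not reaching it is an order of rules rather than a conflict. Section 7.1.3.1 lets the investigator stop treatment without any AE. In a blinded randomized comparison, the graded laboratory tables show a drug effect without needing attribution.

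Most of this stands and limits the point. It does not close the gap: the exception rests on investigator judgement with no numerical threshold, an asymptomatic untreated value meets none of the other routes, and the undefined instruction on clinically relevant changes does not override 8.1.2.

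A reader might infer more than the documents support:

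- **That every disease-associated value is barred from being an AE.** Both sections carry the worse-than-expected exception, and 8.1.3 gives other routes.
- **That such values vanish from the safety evaluation.** Step 5 shows they do not.
- **That the number lost can be estimated** by applying the GT0918-CN-1003 percentages to half of 668, that is 334 subjects per arm. Those are rates of drug-related AEs without a Grade 3 restriction, in mCRPC subjects at 100 to 300 mg. Protocol 2.3 describes that phase 2 prostate cancer setting as 28-day cycles until progression, against 14 days here. Grade 3 or higher AEs of any kind occurred in 14 of 108 subjects there. In the male cohort of the Brazilian COVID-19 study (1.2.3.2), no transaminase rise is listed among TEAEs in at least 10% of GT0918 subjects. No document gives the share that would be attributed to COVID-19.
- **That the AESI comparison is necessarily pulled towards no difference.** Losing drug-caused cases would do that, but the net direction also depends on how many disease-caused rises are excluded in each arm, which is unknown.

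**Conclusion.** The point holds and is minor. The laboratory wording in 7.2.2.3 and 8.1.2 lacks the drug-relatedness exception that 8.1.2 applies to respiratory events, and the two sections use the term clinically significant inconsistently. As a result, an abnormality with two plausible causes can qualify as possibly related and still have no AE record.

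This requires all of the following together: association with COVID-19 in the investigator's view, no judgement that it is worse than expected, no symptoms, no therapy and no treatment change. The loss is confined to AE-based outputs (related TEAEs, AESIs, time to AESI, SAEs) and to reaching the 6.3.1 assessment. The number of subjects affected cannot be computed from the documents.

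**What to change.** For AE recording only, add to the laboratory definition in 7.2.2.3 and to the laboratory bullet in 8.1.2 the exception that 8.1.2 already uses for respiratory events, so that the disease exclusion does not apply when the investigator considers the finding related to study drug. State which causality categories count as related; SAP 4.11.2 already groups possibly, probably and definitely.

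Then reconcile 6.3.1, 7.2.2.3 (including its repeat-testing text and its instruction on clinically relevant changes), 8.1.2 and 8.1.3 with that wording, and use clinically significant in one sense throughout. How repeat testing and 6.3.1 should apply to the newly recorded events is for the sponsor to settle; no rule is proposed here.

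The cost is a protocol amendment with IRB/IEC approval (Section 12) and slightly more laboratory AE entries. The existing laboratory grade and shift tables need no change.

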#### **7.2.2.4 Respiratory Support**

Once enrolled in the study, subjects may be managed with high flow nasal cannula, non-invasive positive pressure ventilation or any other form respiratory support as needed per investigator discretion.

#### **7.2.2.5 Pregnancy and assessment of fertility**

All women of childbearing potential must complete a serum pregnancy test at screening visit, urinary pregnancy test at subsequent visits as per the schedule of assessment. Local laboratories will be used for the analysis of serum and urinary pregnancy tests.

Women who are determined not to be of childbearing potential before the study will only be tested at screening.

For postmenopausal women to be considered “of non-childbearing potential”, subjects should meet the criteria as outlined as following:

Women are considered post-menopausal and not of childbearing potential if they have had 12 months of natural(spontaneous) amenorrhea with appropriate clinical profile (e.g., age appropriate, history of vasomotor symptoms) or have had surgical bilateral oophorectomy (with or without hysterectomy), total hysterectomy or tubal ligation at least six weeks ago. In the case of oophorectomy alone, only when reproductive status of the woman has been confirmed by follow up hormone level assessment is she considered not of child bearing potential.

---

Please refer to Section 8.6 for information on reporting any pregnancies that occur while the subject is on study.

If pregnancy test is performed in between study visits by the subject and the result is positive, the subject must immediately notify the investigator.

### **7.2.3 Pharmacokinetics**

The exposure-response relationship of GT0918 in the treatment of SARS-CoV-2 has not been established. Population PK analyses can be used to further inform dose selection in other populations and support concentration-response investigations with efficacy and safety outcomes. To accomplish this, sparse PK sampling techniques can be employed. Samples will be collected at pre-dose and 2h post first dose, and at pre-dose on Day 3, 7 and 14 from at least 100 subjects who receive intervention and have evaluable PK.

The PK data may be analyzed using validated LC-MS/MS methods with a LLOQ of approximately 5.00 ng/mL for GT0918.

### **7.2.4 Biomarkers**

Blood samples will be collected from all subjects for exploratory biomarker research at the time specified in the SoA where local regulations allow.

The following will be monitored:

- C-reactive protein (CRP)
- Testosterone
- Ferritin
- D-dimer
- Procalcitonin
- Troponin

Samples will be stored and analysis may be performed on biomarkers thought to play a role in immune system related responses to viral infection including, but not limited to, immune pathways, cellular composition, serum analytes, or epigenetic biomarkers, to evaluate their association with observed clinical responses to GT0918 and the disease state.

Samples may be used for research to develop methods, assays, prognostics and/or companion diagnostics related to the intervention target (S protein), the COVID-19 disease state, pathways associated with disease, and/or the mechanism of action of the study intervention.

### **7.2.5 Polymerase Chain Reaction (PCR)**

The second endpoint is the change from baseline to Day 3, 7, 14, 28 in SARS-CoV-2 viral load based on nasopharyngeal swab samples for reverse transcription-polymerase chain reaction (RT-PCR) testing for SARS-CoV-2 (if it is not able to get the samples at each time point, reason should be documented with subject source or eCRF, for example, due to lack of testing supplies, limited testing capacity, subject is able to go clinic or home visit is not able to schedule, etc.).

Quantitative RT-qPCR, which should be done in the central laboratory, is to determine the viral load change from different time points. Samples may additionally be used for exploratory viral RNA sequencing or viral culture. Additional details regarding sample collection and analysis can be found in the laboratory manual.

### **7.2.6 Patient Reported Outcomes**

Subjects will be provided Subject's Diary which will contain the study drug administration information (date/time, with or without meal), and the Symptoms and Overall Clinical Status Subject Questionnaire for subjects to self-evaluate their health status from their own perspective. The questionnaire is required to be completed daily, should at the same time each day (+/- 2 hours for medication scheduling), from screening to end of follow-up at Day 28. Symptoms of COVID-19 are listed per FDA guidance (<https://www.fda.gov/media/142143/download>) and the questionnaire was modified based on this FDA guidance as well, referred to Appendix 5.

The Sponsor and investigators will make efforts to minimize the amount of missing data, include providing reminders (e.g., phone calls, text messages, email) to study subjects to complete Patient Reported Outcomes (PRO) instruments, monitoring compliance with PRO instrument completion throughout the assessment period, following up with study subjects who are not successfully completing PRO instruments (and, where permissible, close contacts if the study subject is not responding), and recording verbal responses for those who are unable to self-record because of illness or other circumstances. Sponsor and investigators/ sites will try to obtain contact information for close contacts of study subjects for use in case of nonresponse. This such close contacts include family member (s) or other close contact when subjects do not respond to follow-up, this process is described in the informed consent document, will be (is) approved by the institutional review board and agreed with subjects. The reasons for missing data should be documented with subject's CRF.

### **7.2.7 Virology**

Characterize the effect of GT0918 compared to placebo on SARS-CoV-2 viral load clearance:

- Change from baseline to Days 3, 7, 14 and 28 in SARS-CoV-2 viral load.
- Proportion of subjects that achieve SARS-CoV-2 clearance (Days 3, 7, 14 and 28)
- Time to SARS-CoV-2 clearance.
- SARS-CoV-2 viral load area under the concentration-time curve (AUC) assessed to Days 3, 7, 14 and 28.

### **7.2.8 Development of resistance**

Characterize emergence of virus resistance to GT0918

- Virus load assessment on Day -1/1(baseline prior to first dose), 3, 7, 14, 28.
- Exploratory endpoints will include:
  - Screening for novel mutants in patients who do not respond to GT0918:
    - Genotype of SARS-CoV-2 viral isolates.

For resistance analyses, include subjects who:

- Are not able to show two consecutive negative test results via RT-PCR testing by Day 28,  
and/or
- Show a positive real-time RT-PCR test result after two consecutive negative RT-PCR test results,  
and/or
- A confirmed rise in SARS-CoV-2 RNA of  $\geq 1$  log10 after achieving nadir on treatment.

Characterize emergence of host resistance to GT0918

- Testosterone levels on Day -1, 3, 7, 14, 28.

